125 pathophysiologic determinants of diabetes: enhance glucose stimulated insulin secretion,  
126 suppress glucagon production, promotes satiety, decreases food intake, improves insulin  
127 sensitivity, lower ectopic fat deposition (i.e. liver steatosis, visceral fat), etc. GLP-1  
128 agonists lower HbA1c by 1.5-2%, have a very low risk of hypoglycemia, and promote  
129 weight loss – all very desirable effects in patients with type 2 diabetes [35]. While this

130 treatment does require an injection, it is very easy to use, does not require continuous  
131 treatment titration, and greatly reduces the need for frequent glucose self-monitoring. All  
132 these attributes make it quite an appealing treatment alternative for patients with type 2  
133 diabetes. In the current diabetes treatment guidelines it is recommended as a second or  
134 third line agent after metformin failure.

135

136 8. The combination of basal insulin and GLP-1 agonists has been proven to be safe and  
137 very effective.

138 A meta-analysis of pooled data from across the LEAD program demonstrated that in  
139 patients with baseline HbA1c of > 9% liraglutide was better than glargine as an add on to  
140 oral hypoglycemic medications with average reduction in HbA1c of 1.9% [39]. Several  
141 other studies support equal or superior HbA1c reduction when a GLP-1 agonist is added  
142 to background therapy and compared to basal insulin, with the additional benefit of  
143 weight loss and minimal hypoglycemia [40-43]. GLP-1 agonist has also demonstrated  
144 superiority when added to maximized basal insulin therapy and metformin, when  
145 compared to prandial insulin alone [40, 44-48]. Furthermore, treatment with GLP-1  
146 agonist in combination with basal insulin was shown to have a synergistic effect on  
147 glycemic control, with GLP-1 agonists exerting an insulin sparing effect, as well as  
148 ameliorating or eliminating the undesirable weight gain associated with insulin therapy.

149

150 The current evidence suggests the combination of metformin, GLP-1 agonist, and basal  
151 insulin to be the most effective and simple strategy to achieve near normal glycemia in  
152 patients with a baseline HbA1c < 10%, while avoiding the side effects of weight gain,  
153 complexity of care, and hypoglycemia associated with insulin alone, or post-prandial  
154 hyperglycemia, weight gain, and hypoglycemia from the association of basal insulin to  

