## 211 **Specific aims:**

- 212 1. Compare the two treatment regimens with respect to a disease and patient-  
213 relevant composite outcome of effectiveness (HbA1c <7%) and safety (no  
214 hypoglycemia and no weight gain);
- 215 2. Compare the two treatment regimens with respect to treatment burden (number of  
216 daily shots, amount of glucose self-monitoring, need for treatment titration);
- 217 3. Compare the two treatment regimens with respect to quality of life [as measured  
218 by a disease specific (DQOL) questionnaire and general health (SF-36)  
219 questionnaire];

220 4. Compare the two treatment regimens with respect to all healthcare related costs:  
221 actual cost of the pharmacologic agents, glucose monitoring supplies, all other  
222 pharmacologic (non-study related) and non-pharmacologic healthcare related  
223 costs (outpatient and inpatient, diabetes related and non-diabetes related). We will  
224 also compare actual physician time spent during office visits and non-visit related  
225 care of these patients. While no actual dollar amount can be attached to this  
226 (phone visits and longer office visits required by the need for extra patient  
227 education are not customarily reimbursable) time commitment is of great  
228 relevance to our physicians who care for these very complex patients.  
229

230 **Primary outcome:**

231 Change in HbA1c from randomization to 26 weeks of therapy.  
232

233 **Secondary outcomes:**

- 234 1. The main secondary outcome is a less traditional but very patient-centric and  
235 clinically meaningful composite outcome of HbA1c <7% AND no documented  
236 hypoglycemia (capillary glucose level <56 mg/dl) AND no significant weight  
237 gain (<3% body weight) during the 6-mo study follow-up;
- 238 2. % reaching target HbA1c of <7% at end of study;
- 239 3. 7-point glucose profile results;
- 240 4. % patients reaching pre-specified “treatment failure” outcome;
- 241 5. Change in weight from baseline (both absolute weight lost and percent of body  
242 weight);
- 243 6. % patients with weight loss >5% of body weight;
- 244 7. Number of hypoglycemic episodes defined as mild (symptoms of hypoglycemia  
245 confirmed by a CBG reading of <70 mg/dl), moderate (any CBG reading <56  
246 mg/dl), severe (need for help to recover regardless of CBG reading);
- 247 8. Number of patients experiencing any hypoglycemic episodes;
- 248 9. DQOL questionnaire score;
- 249 10. SF-36 questionnaire score;

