#### 425 *Follow-up visits:*

426 At 1-, 3-, and 6-months (visits 4, 5, 6) patients will be followed-up in person for interim  
427 (and end of study, respectively) evaluations of all outcome parameters, as well as

428 protocol-driven treatment titration. A 7-point glucose profile will be repeated prior to the  
 429 last visit in the study.

430

431 **Interventions:**

432 Both groups will either continue or initiate treatment with metformin. To minimize  
 433 gastrointestinal side effects metformin will be initiated at 500 mg daily (or continued at  
 434 current dose) and titrated weekly in 500 mg increments to the final dose of 1000 mg  
 435 twice daily (or maximum tolerated dose which should be at least 500 mg BID).

436

437 Both groups will be initiated on basal insulin detemir. If new to insulin, this will be  
 438 started at 0.3 units/kg once daily at bedtime and self-titrated based on the study protocol  
 439 (see detemir patient self-titration table). If already on basal insulin, will take the total  
 440 daily dose of basal insulin and perform a 1:1 dose conversion to insulin detemir, which  
 441 will be administered once daily at bedtime, followed by the same titration. Additionally,  
 442 physician-directed titration will occur, if needed, during the scheduled phone and/or  
 443 office visits, as well as any unscheduled patient-initiated visits (phone/in person, if  
 444 applicable). All patients new to insulin will be seen by the diabetes educator to receive  
 445 instruction in insulin injection techniques.

446

447 Detemir patient self-titration table:

Fasting Blood glucose	Change in your insulin dose
<45	Decrease by 5 units
<70 mg/dL	Decrease by 3 units
71- 100 mg/dL	No change in your insulin dose
101-120 mg/dL	Increase by 1 units

448

449 Patients randomized to liraglutide will stop any insulin products besides detemir (if  
 450 applicable), initiate liraglutide at 0.6 mg/day, and dose escalate weekly to 1.2 mg/dl and  
 451 final dose of 1.8 mg/dl. Patients who develop significant and persistent gastrointestinal  
 452 side effects are allowed to down-titrate the dose of liraglutide to 1.2 mg/dl for 1 week  
 453 or until the side effect resolve.

454

455 Patients randomized to meal-time insulin will initiate insulin aspart before each meal.  
 456 Aspart insulin will be initiated at a dose of 0.3 units/kg/day divided among the number of  

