 457 meals taken daily. Meal-time insulin titration, if needed, can be either patient driven (see  
 458 table below) or physician-directed during the scheduled follow-up visits (phone or in  
 459 person), as well as any unscheduled patient-initiated visits (if applicable).

460

461 Novolog patient self-titration table:

Glucose prior to lunch	Change in breakfast insulin dose	Glucose prior to dinner	Change in lunch insulin dose	Glucose prior to bedtime	Change in dinner insulin dose
<54	-2 units	<54	-2 units	<54	-2 units
55-69	-1 unit	55-69	-1 unit	55-69	-1 unit
70-120	No change	70-120	No change	70-130	No change
121-160	+1 unit	121-160	+1 unit	131-180	+1 unit

>160	+2 units	>160	+2 units	>180	+2 units
------	----------	------	----------	------	----------

462

463 **Rescue therapy:**

464 Should any patients randomized to liraglutide treatment experience persistent  
465 hyperglycemia (defined as a confirmed Hb1c>10%) at the 3-mo visit (visit 5), meal-time  
466 insulin aspart will be initiated per the same protocol as above. This is a pre-specified  
467 “treatment failure” end-point. Following initiation of rescue therapy patients will  
468 continue all scheduled visits and procedures through the end of the trial.

469

470 Should any patients randomized to the “standard of care” group experience persistent  
471 hyperglycemia (defined as a confirmed HbA1c >10%) at the 3-mo visit (visit 5),  
472 treatment and insulin titration will continue as scheduled. This is also a pre-specified  
473 “treatment failure” end-point.

474

475 A graphical review of the visit procedures and timing is presented below:

Visit	1	2	3	4	5	6
Time	3-7	0	2 weeks	1	3	6
Type	Office	Office	Phone	Office	Office	Office
Consent	x					
I&E criteria	x					
Randomization criteria		x				
Randomization		x				
Physical exam	x			x	x	x
Height	x					
Vitals (weight, BP, pulse)	x	x		x	x	x
Dietary counseling	x	x	x	x	x	x
Lifestyle counseling	x	x	x	x	x	x
7-point glucose		x				x
Labs (HbA1c, lipids, CMP, Hb)	x				x	x
Dispense trial drug		x		x	x	
Hypoglycemia assessment	X	X	X	x	x	x
Frequency of glucose monitoring				x	x	x
Titrate insulin		x	x	x	x	
Liraglutide titration (if applicable)			x			
Insulin dose assessment		x	x	x	x	x
Compliance assessment				x	x	x
# daily injections				x	x	x
QoL questionnaires (DQOL and SF36)		x				x
AE and SAE assessment		x	x	x	x	x
Pregnancy test (if needed)	x	x		x	x	x
Physician time assessment		x	x	x	x	x

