513 All safety assessments are performed at each visit, in person or by phone. Any  
514 unanticipated or serious adverse events will be reported to the local IRB and FDA in  
515 accordance with local guidelines.

516

- 517 1. Hypoglycemia – All plasma glucose values  $\leq 70$  mg/dL, as well as values  $>70$   
518 mg/dL when hypoglycemic symptoms have occurred, should be recorded by the  
519 subjects in the blood glucose diaries provided at each visit. The recording should  
520 include:

- 521 • date of hypoglycemic episode

- 522 • time of hypoglycemic episode
- 523 • time of last main meal prior to episode
- 524 • whether the episode was symptomatic
- 525 • whether the episode was in relation to exercise
- 526 • whether seizure or coma developed
- 527 • whether the subject was able to treat him/herself
- 528 • the plasma glucose level before treating the episode

529

530 The following definitions for hypoglycemia will be used:

- 531 • Mild- Symptomatic or asymptomatic hypoglycemia with blood glucose 56-69
- 532 mg/dl and subject was able to treat him/herself
- 533 • Moderate- Symptomatic or asymptomatic hypoglycemia with blood glucose <56
- 534 mg/dl and subject was able to treat him/herself
- 535 • Severe- Blood sugar <70 mg/dl or symptoms highly suggestive of hypoglycemia
- 536 and the subject needed assistance to be treated with carbohydrates, glucagon, or
- 537 other resuscitative actions
- 538 • Nocturnal hypoglycaemia- blood glucose <70 with a time of onset between 00:01
- 539 and 05:59 (both included)
- 540 • Relative Hypoglycemia- Blood glucose >69 mg/dl with symptoms highly
- 541 suggestive of hypoglycemia
- 542 • Probable symptomatic hypoglycemia- Symptoms highly suggestive of
- 543 hypoglycemia but subject did not measure blood glucose.

544

545 2. Other treatment specific side effects

- 546 • Nausea, vomiting, diarrhea, and headache;
- 547 • Abdominal pain suspicious for pancreatitis would prompt immediate physician
- 548 evaluation and laboratory testing for amylase and lipase measurement which
- 549 would be processed immediately and analysed by PHHS Clinical Laboratory.

- 550 3. Pregnancy Test- females of childbearing potential will have urine pregnancy test
- 551 (human chorionic gonadotropin, hCG) performed if clinically indicated in the
- 552 assessment of the investigator. Urine-stick pregnancy test will be performed for
- 553 females of childbearing potential at any time during the trial, if a menstrual period is

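### Any asymptomatic reading below 56 mg/dl fails the main secondary composite, so if the aspart arm self-tests more often the composite is biased toward liraglutide

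*Combined protocol and SAP*

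**What the plan says.** Secondary outcomes, item 1, defines the main secondary outcome as HbA1c below 7%, no documented "hypoglycemia (capillary glucose level <56 mg/dl) AND no significant weight" gain of 3% or more, over the six-month follow-up. No symptom is required. Item 7 grades episodes: mild is symptoms "confirmed by a CBG reading of <70 mg/dl), moderate (any CBG reading <56" mg/dl), and severe is needing help. Assessments for Safety has "Moderate- Symptomatic or asymptomatic hypoglycemia with blood glucose <56" mg/dl, and its mild grade (56-69 mg/dl) also admits asymptomatic readings, unlike item 7. Item 8 counts patients with any episode.

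Under Interventions, both arms self-titrate detemir from a table headed "Fasting Blood glucose". The aspart arm has a second table, whose first column is "Glucose prior to lunch", followed by pre-dinner and bedtime values. Its use is qualified: "meals taken daily. Meal-time insulin titration, if needed, can be either patient driven (see" the table) or directed by the physician.

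Background item 7 says that GLP-1 treatment does not need continuous "treatment titration, and greatly reduces the need for frequent glucose self-monitoring". Specific aim 2 compares the amount of self-monitoring as treatment burden, and outcomes 15-16 count the checks. Apart from the 7-point profiles before visits 2 and 6, no testing schedule is set for either arm. Patients use their own meters and know their treatment.

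The Statistical Analysis Plan compares the composite by logistic regression and summarises hypoglycemic events descriptively. It does not mention testing frequency in connection with either.

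**The concern.** A symptomatic low is likely to prompt a test in either arm. An asymptomatic one is documented only if a routine test falls at that moment. The number of routine tests is therefore the number of chances to fail the composite, and the protocol gives one arm more reasons to test. If testing differs as the plan expects, two arms with the same true risk would show different rates of documented hypoglycemia, and the difference would favour liraglutide.

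At stake is how a positive result on the main secondary outcome is read. The plan hopes for two benefits, less self-monitoring and less hypoglycemia. As defined, the first can generate part of the second. The moderate grade in outcome 7 and the any-episode count in outcome 8 are exposed in the same way.

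**Working it through.** **The plan's own figure.** Sample Size Calculation states at least 80% power for the composite at 25% versus 5%, two-sided alpha 0.05. The pooled normal formula gives 0.756 at 44 per arm and 0.809 at 50. Exact enumeration at 44 per arm gives 0.804 for both the chi-square and the likelihood-ratio test. The statement reproduces with 50 randomized per arm, or with 44 completers under those two tests. The point here is ascertainment, not power.

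**Inputs from the documents.** The detemir table uses one time of day (fasting). The aspart table adds three (before lunch, before dinner, bedtime). Tables alone therefore imply at most 4 versus 1. There are 44 completers per arm and 26 weeks (182 days) of follow-up.

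**Assumptions, since the documents give no values.** True risk is equal in both arms.
- A = probability of meeting the HbA1c and weight components, 0.25 or 0.40, independent of lows.
- L = expected readings below 56 mg/dl per patient per time of day over 26 weeks if tested throughout, 0.05 to 0.6.
- f = share of the non-fasting lows that liraglutide patients also catch, 0 to 0.8.

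**Formulas.** The expected number of detected lows is 4L on aspart and (1 + 3f)L on liraglutide. P(no documented low) = exp(-expected number). Composite = A x P(no documented low).

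**Middle case, A = 0.40, L = 0.2, f = 0.3.**
- Aspart: exp(-0.8) = 0.449, so 55% have a documented low; composite 0.40 x 0.449 = 18.0%.
- Liraglutide: exp(-1.9 x 0.2) = exp(-0.38) = 0.684, so 32% have one; composite 0.40 x 0.684 = 27.4%.

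| A, L, f | Documented low, aspart vs liraglutide | Composite, aspart vs liraglutide | Spurious difference (points) | Chance of a significant result for liraglutide, 44 per arm |
|---|---|---|---|---|
| 0.25, 0.05, 0.8 | 18% vs 16% | 20.5% vs 21.1% | 0.6 | 3.2% |
| 0.40, 0.2, 0.3 | 55% vs 32% | 18.0% vs 27.4% | 9.4 | 18.8% |
| 0.40, 0.4, 0 | 80% vs 33% | 8.1% vs 26.8% | 18.7 | 67.5% |

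The last column is from exact enumeration of the chi-square test; the nominal value is 2.5%. Over all settings tried it runs from about 2% to 80%. With equal testing (f = 1) the spurious difference is 0.

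**Cross-check per reading.** Take p as the chance that any reading is below 56 mg/dl, with 4 versus 1 readings a day and 30% meeting the other components. P(no low) = (1 - p)^(182 x readings per day).
- p = 0.05%: documented low 31% vs 9%; composite 21% vs 27%.
- p = 0.1%: 52% vs 17%; composite 14% vs 25%.
- p = 0.2%: 77% vs 31%; composite 7% vs 21%.

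These treat readings as independent. If lows cluster in particular patients (gamma frailty, shape 0.5), P(no low) = (1 + m/0.5)^(-0.5), where m is the expected number of lows. At p = 0.2%, m = 728 x 0.002 = 1.456 on aspart and 182 x 0.002 = 0.364 on liraglutide. Documented lows become 49% vs 24% and the composite 15% vs 23%, so the gap falls from about 14 to about 8 points.

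**The case against.** - **No arm is instructed to test at set times.** A reader might infer from the tables that aspart patients must test four times a day and liraglutide patients once. The documents do not say so: meal-time titration happens only when required and can be left to the physician. This stands, and 4 versus 1 is an upper case.
- **The direction is not guaranteed.** A reader might take the plan's expectation of less monitoring as settling the matter. It is a general remark about GLP-1 agonists, both arms here titrate detemir, and aim 2 only proposes a comparison. This stands too: the bias is conditional on the aspart arm testing more.
- **Some features work the other way.** The aspart table lowers the dose after readings under 70, so testing may prevent later lows. Liraglutide patients with confirmed HbA1c above 10% at month 3 start aspart under the same protocol, which narrows the testing gap. Both may shrink the bias; neither equalises detection in general.
- **It is partly handled.** Outcome 7 has a symptom-based mild grade and a severe grade, and outcomes 15-16 would reveal unequal testing. That helps a reader notice a problem, but the composite has no symptom-based version, so its dependence on testing could not be judged.
- **Symptom-based counting has its own bias.** Patients are unblinded and report their own symptoms. This is correct, and it is why such a version can support the all-readings result but not replace it.

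**Conclusion.** The concern holds conditionally. The definition of the composite, the differing titration tables and the absence of any testing-related analysis are all in the text. If the aspart arm tests more often, asymptomatic lows will be detected more often there, and the composite and the moderate and any-episode counts will lean toward liraglutide.

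The size is unknown. The range of about 0.6 to 19 points rests on assumed rates of low readings, assumed testing and equal true risk. Its lower end is negligible. A reader might infer from the upper end that the planned 25% versus 5% could be an artefact of testing alone. The documents do not support that: it needs the most extreme assumptions, and any true difference in hypoglycemia would add to the bias. The primary HbA1c comparison is unaffected.

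**What to change.** Keep the all-readings composite as defined. Pre-specify one supporting analysis of the composite and of outcomes 7-8 that counts only episodes with symptoms plus a capillary reading below 56 mg/dl, and severe episodes. The diary already asks about symptoms and whether the patient could treat the episode unaided. A symptomatic definition also appears in the title of the lixisenatide composite-outcome study that the plan cites (reference 44).

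Report this beside the main result, with readings per day by arm. State in advance that a composite benefit seen only in the all-readings version will not be attributed to less hypoglycemia. No formal rule that the versions must agree is needed.

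A comparison of fasting readings could be added descriptively if individual meter or diary values are kept; the protocol specifies only average readings per day from the download. It would largely miss daytime lows.

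Two alternatives are not worth adding as evidence. The final 7-point profile would yield about 7 x 44 x 0.002 = 0.6 lows per arm even at the highest per-reading rate used above. Lows per 1,000 readings conditions on testing, which treatment itself affects.

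The cost is SAP wording and a small extra analysis. The drawback is that the symptomatic version misses genuine asymptomatic lows and relies on unblinded report, so it may show a smaller difference.

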### 295 **Rationale for study Design**

- 296 • The randomized design, with stratification for pertinent variables, will allow us to  
297 fully compare the effects of the two treatment algorithms in this hard to treat  
298 patient population.
- 299 • A 3-7 day run-in period was introduced in order to ensure patient compliance with  
300 study procedures prior to randomization.
- 301 • The patient-guided titration schedule for basal insulin is well validated in the  
302 literature and should help to lower fasting glucose level within a shorter period of  
303 time.
- 304 • A 6-month intervention period was chosen as nadir HbA1c after initiation of a  
305 treatment regimen is achieved by this time, therefore allowing us to evaluate the  
306 full effectiveness of these interventions.

307

### 308 **Study Population:**

#### 309 Inclusion Criteria:

- 310 1. Informed consent obtained before any trial-related activities;
- 311 2. Both genders and all ethnicities;
- 312 3. Currently receiving medical care at Parkland Health and Hospital System (PHHS),  
313 Dallas, TX;
- 314 3. Age  $\geq$  18 years;
- 315 4. Diagnosis of Type-2 Diabetes, regardless of time since diagnosis;
- 316 5. Confirmed HbA1c  $>10\%$ .

317

318

#### 319 *Exclusion criteria:*

- 320 1. Age  $<18$  as the feasibility and safety of this treatment regimen should be first  
321 established in the adult population; if successful, a subsequent pediatric study will  
322 be proposed;
- 323 2. Current use (within the past 30 days) of prandial-insulin;
- 324 3. Current use (within the past 30 days) of GLP-1 analogues or DPP-4 inhibitors;
- 325 4. Type 1 diabetes as purposefully withholding meal-time insulin is contraindicated;
- 326 5. Clinical state requiring inpatient admission/treatment;
- 327 6. Contraindication or strong cautions to any of the study medications:
  - 328 a. eGFR  $<30$  ml/min if already on metformin, or eGFR  $<45$  ml/min is not  
329 currently on metformin (per metformin label)
  - 330 b. History of lactic acidosis (per metformin label)
  - 331 c. Advanced hepatic or cardiac disease (per metformin label)
  - 332 d. Age  $>80$  years (per metformin label)
  - 333 e. Chronic alcohol use ( $>14$  drinks/week)
  - 334 f. History of pancreatitis (per liraglutide label)
  - 335 g. Personal or family history of medullary thyroid cancer or MEN syndrome  
336 (per liraglutide label)

- 337 h. Pregnancy, intention of becoming pregnant, or lactation (per liraglutide  
338 label)  
339 i. Female of reproductive age not using adequate contraceptive methods (per  
340 liraglutide label). Adequate contraceptive measures include sterilization,  
341 intrauterine devices, oral contraceptives, approved hormonal implant,  
342 diaphragm with spermicide or condom with spermicide;  
343 7. Any serious or unstable medical condition as it would interfere with treatment  
344 assignment as well as outcome measurement;  
345 8. Any scheduled elective procedures/surgeries;  
346 9. Active infections, including osteomyelitis;  
347 10. Not willing to participate, unable to keep projected appointments, unwillingness  
348 to receive injectable treatment;  
349 11. Known or suspected allergy to any of the trial products or related products;  
350 12. Prior participation in this or another trial, or receipt of any investigational drugs  
351 within 3 months prior to screening;  
352 13. Non-English speaking patients are excluded for safety reasons.  
353

